## 7.7. Other Ophthalmology Imaging Assessments

Unless otherwise stated, ocular imaging data collected will be listed by treatment group and overall for the Safety set. The summary will be performed separately by study eye and by fellow eye. The ophthalmology imaging assessments performed in this study include the following:

- Digital Color Fundus Photographs (DCFP)
  - Shift from baseline in the presence/absence of hemorrhage at each visit
- FA
  - The following analyses will be performed in all study eyes and in non-study eyes without a history of CNV at baseline (in medical history) in the corresponding eye.
    - Incidence of new CNV. This will be summarized as the cumulative number of CNV events by each visit and the cumulative incidence by that visit based on Kaplan Meier methods.
    - Incidence of new CNV by type (classic, occult, classic & occult, disciform scar) at first emergence will be summarized at each visit for the cumulative number of events.
    - Total CNV size (diameter) at first emergence will be summarized at each visit for the cumulative number of events.
- SD-OCT
  - Descriptive statistics on central subfield thickness at each visit
  - Plot of the mean change from baseline in central subfield thickness in the study eye  $\pm$  the standard error over time by treatment group.
  - Descriptive statistics on central (center point) retinal thickness at each visit
  - Shift from baseline in the presence/absence of subretinal fluid at each visit
  - Shift from baseline in the presence/absence of cystoid spaces at each visit
- Specular Microscopy

- Endothelial Cell Count is assessed using specular microscopy, and the change from baseline in cell density (cells/mm^2) as well as the change from baseline in average cell-size will be summarized with descriptive statistics.
- OCT-A
  - Incidence of subclinical CNV (referred to as MNV in the datasets) determined by OCT-A in eyes without previous CNV reported in the medical history or as an adverse event in the corresponding eye at each visit.

In addition, the following summary of suspected and reading-center confirmed CNV cases will be presented by treatment group. This will be presented separately for the study eye only.

- The number and percentage of subjects with an Exudative AMD TEAE on or before Month 12 (or Month 24 if the final analysis)
- The number and percentage of subjects with at least one suspected new onset CNV case submitted to the reading center by the Investigator post-baseline through Month 12 (or Month 24 if the final analysis)
- The number and percentage of subjects with a reading-center confirmed new onset CNV case (out of the suspected CNV cases submitted by the Investigator) post-baseline through Month 12 (or Month 24 if the final analysis). Reading-center confirmed CNV case is identified as either:
  - Presence of CNV on FA (Type = classic, occult, classic & occult, disciform scar) OR
  - Presence of CNV thickness on SD-OCT
- The number and percentage of subjects with a reading-center confirmed new onset CNV case (out of the suspected CNV cases submitted by the Investigator) post-baseline through Month 12 (or Month 24 if the final analysis) and also reported as an Exudative AMD TEAE.
- The number and percentage of subjects with a reading-center confirmed new onset CNV case (out of the suspected CNV cases submitted by the Investigator) post-baseline through Month 12 (or Month 24 if the final analysis) without an Exudative AMD TEAE ever reported.
- The number and percentage of subjects with at least one suspected CNV case, confirmed by the reading-center but previously reported as an Exudative AMD TEAE.
- The number and percentage of subjects with at least one suspected CNV case, not confirmed by the reading-center but still reported as an Exudative AMD TEAE.
- The number and percentage of subjects with a reading-center finding of presence of new-onset CNV (defined in the same way as a confirmed new onset CNV case) without any other submission to the reading center of a suspected case post-baseline through Month 12 (or Month 24 if the final analysis) and also reported as an Exudative AMD TEAE on or before Month 12 (or Month 24 if the final analysis)

- The number and percentage of subjects with a reading-center finding of presence of new-onset CNV (defined in the same way as a confirmed new onset CNV case) without any other submission to the reading center of a suspected case post-baseline through Month 12 (or Month 24 if the final analysis) and no report of an Exudative AMD TEAE.
- The number and percentage of subjects with Exudative AMD TEAE and without a suspected case submitted to the reading center as well as without a reading center finding of new-onset CNV (defined in the same way as a confirmed new onset CNV case).

## **7.8. Immunogenicity**

Immunogenicity data will be listed separately for anti-pegcetacoplan peptide antibody and anti-PEG antibody results. The number and percentage of samples confirmed positive for ADA response will be summarized by treatment groups (i.e., PM, PEOM, and Sham). The number and percentage of subjects with treatment-emergent and treatment-boosted responses will be presented by treatment group. Treatment emergent response is defined as a confirmed positive antibody result postdose after a negative antibody result reported at baseline. Treatment-boosted response is defined as a  $\geq 4$ -fold increase in titer from the baseline level.

## **7.9. Death**

Subject deaths and primary cause of death will be summarized.

## **7.10. Other Safety Data**

Urine pregnancy test will be provided in a listing.

## **8. PHARMACOKINETICS ANALYSIS**

No pharmacokinetic analyses are planned for this study.

## **9. PHARMACODYNAMIC ANALYSES**

No pharmacodynamic analyses are planned for this study.

## **10. OTHER ANALYSES**

No other analyses are planned for this study.

## **11. INTERIM ANALYSIS**

No formal interim analyses are planned for this study.

To support regulatory submissions, data cuts of the Month 12 – Month 24 data of the study may be taken prior to the final database lock and summarized prior to the final study reporting.

The analysis of this data will not be used to modify the pre-planned analyses of this study.

## **12. DATA MONITORING COMMITTEE**

An external, independent DMC reviews unmasked data across the conduct of the study approximately every 6 months. A charter for the DMC as well as a DMC statistical analysis plan was prepared separately.

## **13. DATA HANDLING CONVENTIONS**

### **13.1. General Data Reporting Conventions**

Continuous variables will be summarized using the number of non-missing observations (n), mean, SD, median, quartile 1, quartile 3, minimum, and maximum. Categorical variables will be summarized using frequencies and percentages. Unless stated otherwise, for all percentages, the number of subjects in the analysis population for the treatment group will be the denominator.

Unless otherwise specified, the estimated mean and median for a set of values should be printed out to 1 more decimal place than the original values, and standard deviations should be printed out to 2 more decimal places than the original values. The minimum and maximum should report the same number of decimal places as the original values. Percentages will be displayed with 1 decimal place; except percentages will not be presented when the count is zero and 100% will be presented as an integer.

### **13.2. Definition of Baseline**

Unless stated otherwise, baseline will be defined as the last available pre-treatment value taken on or before the first dose date of study drug, and will be used for summary of baseline characteristics, as well as for all change-from-baseline analyses of efficacy and safety endpoints.

### **13.3. Definition of Relative Study Days**

Unless otherwise noted, relative study days (Rel Days) of an evaluation are defined as number of days relative to the first dose date of study drug which is designated as Day 1, and the preceding day is Day -1, the day before that is Day -2, etc.

If evaluation date is on or after first dose date, then relative study days are calculated as

$$\text{Evaluation date} - \text{first dose date of study drug} + 1.$$

If evaluation date is before first dose date, then relative study days are calculated as

$$\text{Evaluation date} - \text{first dose date of study drug}$$

Relative study days take negative values if evaluation date occurs prior to first dose date and take positive values if evaluation date occurs on or after first dose date of study drug.

### **13.4. Definition of Visit Windows**

#### **13.4.1. All Assessments Except Microperimetry**

All assessments occurring on or before the first date of dosing (Analysis Study Day (ADY)  $\leq 1$ ) will be assigned to the Baseline analysis visit window.

Unless otherwise specified, the actual scheduled nominal post-baseline visit will be used for over time summaries. Post-baseline unscheduled visits and early termination visits will be mapped to a scheduled visit and will only be used in the analysis if the nominal scheduled visit result is missing, [Table 5](#) and [Table 6](#) presents the analysis visit window mapping for unscheduled and early term visits. In the case that multiple unscheduled or early termination visits are in the same analysis window, the one closest to the target date will be used. In the event that windowed visit

is mapped to an illogical sequence of visits when considering nearby scheduled visits (i.e., windowed visit is higher than the subsequent visit or lower than the preceding visit), the windowed visit will be set to the logical scheduled visit.

**Table 5: Post-Baseline Analysis Visit Window for Unscheduled and Early Termination Visits: All Assessments Except Microperimetry: Monthly Regimen**

Analysis Visit	Target Study Day	Analysis Window (days)
Month 1	30	2 to 45
Month 2	60	46 to 75
Month 3	90	76 to 105
Month 4	120	106 to 135
Month 5	150	136 to 165
Month 6	180	166 to 195
Month 7	210	196 to 225
Month 8	240	226 to 255
Month 9	270	256 to 285
Month 10	300	286 to 315
Month 11	330	316 to 345
Month 12	360	346 to 375
Month 13	390	376 to 405
Month 14	420	406 to 435
Month 15	450	436 to 465
Month 16	480	466 to 495
Month 17	510	496 to 525
Month 18	540	526 to 555
Month 19	570	556 to 585
Month 20	600	586 to 615
Month 21	630	616 to 645
Month 22	660	646 to 675
Month 23	690	676 to 705
Month 24	720	706 to EOS

**Table 6: Post-Baseline Analysis Visit Window for Unscheduled and Early Termination Visits: All Assessments Except Microperimetry: Every Other Month Regimen**

Analysis Visit	Target Study Day	Analysis Window (days)
Month 1	30	2 to 45
Month 2	60	46 to 75
Month 3	90	76 to 105
Month 4	120	106 to 135
Month 5	150	136 to 165
Month 6	180	166 to 195
Month 7	210	196 to 225
Month 8	240	226 to 255
Month 9	270	256 to 285
Month 10	300	286 to 315
Month 11	330	316 to 345
Month 12	360	346 to 375
Month 14	420	376 to 450
Month 16	480	451 to 510
Month 18	540	511 to 570
Month 20	600	571 to 630
Month 22	660	631 to 690
Month 24	720	690 to EOS

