7.3.2. Treatment Administration

Only qualified study staff and those delegated the responsibility of study drug administration on the delegation of authority log should perform this procedure. All staff should be appropriately trained on all procedures prior to performing the procedures. Sites should follow the Visit Schedule for order of procedures and assessments.

Administration of study treatment (pegcetacoplan or sham) can be done on a separate day from the assessment visit if both days fall within the visit window. If this occurs on the randomization

visit, then the administration of pegcetacoplan or sham should be done within 3 days of randomization and after approval from the medical monitor. When study treatment administration is on a day other than a study visit, then the only assessment that must be done on the day of study treatment administration is the IOP preinjection.

If a subject falls outside the visit window for a dosing visit, the dose should be skipped and the subject should be scheduled on time for the next dosing visit.

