16. APPENDICES

APPENDIX A: VISIT SCHEDULE—Monthly Group—Screening, Day 1 through Month 12

	Screening Treatment														
Visit #	1	2	3	4	5	6	7	8	9	10	11	12	13	14	
Day	−28 to −1	1	30	60	90	120	150	180	210	240	270	300	330	360	Early
Week	0	0	4	8	12	16	20	24	28	32	36	40	44	48	Term ^A
Month	0	0	1	2	3	4	5	6	7	8	9	10	11	12	
Window (+ or – days)	2	0	8	8	8	8	8	8	8	8	8	8	8	8	
Informed consent / assign screening number	X														
Demographic data	X														
Inclusion/exclusion criteria ^B	X	X													
Medical/surgical/ocular history ^C	X														
Blood draw—safety labs ^{D,E,F}	X	X		X				X						X	X
Urine sample collection ^{D, E,F}	X	X		X				X						X	X
Urine pregnancy test ^{D,E,F}		X	X	X	X	X	X	X	X	X	X	X	X	X	
Blood draw—anti-pegcetacoplan Ab ^D		X	X	X				X						X	X
Blood draw—genotyping (if applicable) ^D				X											
Blood draw for clinical repository (if applicable) ^{D,G}				x				x						x	x
Vital signs ^H	X	X	X	X	X	X	X	X	X	X	X	X	X	X	X
Physical examination ^I	X													X	X
BCVA J	X	X	X	X	X	X	X	X	X	X	X	X	X	X	X
LL-BCVA ^J		X	X	X	X	X	X	X	X	X	X	X	X	X	X
MNREAD or Radner Reading Charts (select countries) ^{J,K}		x						x						x	x
Mesopic microperimetry ^L	X							SE						X	X
Slitlamp examination	X	X	X	X	X	X	X	X	X	X	X	X	X	X	X
Endothelial cell count ^S		X						X						X	X
NEI VFQ-25 M		X						X						X	X
FRI M		X						X						X	X
Home-based digital applications M,N,S		X	X	X	X			X						X	
Dilated indirect ophthalmoscopy	X	X	X	X	X	X	X	X	X	X	X	X	X	X	X
IOP measurement	X	X	X	X	X	X	X	X	X	X	X	X	X	X	X

	Screening						T	reatme	nt						
Visit #	1	2	3	4	5	6	7	8	9	10	11	12	13	14	
Day	−28 to −1	1	30	60	90	120	150	180	210	240	270	300	330	360	Early
Week	0	0	4	8	12	16	20	24	28	32	36	40	44	48	Term ^A
Month	0	0	1	2	3	4	5	6	7	8	9	10	11	12	
Window (+ or – days)	2	0	8	8	8	8	8	8	8	8	8	8	8	8	
SD-OCT O	X	X	X	X	X	X	X	X	X	X	X	X	X	X	X
FAF ⁰	X	X		SE		SE		X		SE		SE		X	X
NIR ⁰	X	X		SE		SE		X		SE		SE		X	X
DCFP O	X													X	X
FFA ⁰	X													X	X
OCT-A ^S		xS						xS						x S	X
Study eye determination	X														
Randomization		X													
Pegcetacoplan administration or Sham Injection ^T		x	x	x	x	x	x	x	x	x	x	x	x	x	
Postinjection assessment P		X	X	X	X	X	X	X	X	X	X	X	X	X	
Follow-up call ^Q		X	X	X	X										
Concomitant medication/ concomitant ocular procedures ^R	x	x	x	x	x	x	x	x	x	x	x	x	x	x	x
Adverse events	X	X	X	X	X	X	X	X	X	X	X	X	X	X	X

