APPENDIX K: PROTOCOL CHANGES TO BE FOLLOWED DURING COVID-19 RESTRICTIONS

OVERVIEW

In response to the COVID-19 crisis, to ensure the safety of study subjects and Investigative Sites as well as proper conduct of the study, TEMPORARY changes to the protocol have been implemented. These changes should be followed only during COVID-19 restrictions and include extended IP administration windows, changes to masking rules, rescreening instructions, and a revised schedule of assessments.

Where feasible, sites could continue to follow the full schedule of assessments (based on their treatment group assignment).

EXTENDED IP ADMINISTRATION WINDOWS

In order to allow more flexibility to sites and subjects, and to potentially mitigate missed IP administration, an extended IP administration window can be followed. The extended window can ONLY be used in situations related to COVID-19 restrictions and after medical monitor approval. Footnote "T" of each COVID-19 assessment table below reflects these extended IP options.

Per protocol, the study window is as followed:

- Monthly treatment group: +/–8 days for the entire study duration
- EOM treatment group: +/-8 days for the first study year and +/-16 days for the second study year

During COVID-19 restrictions, the IP administration window can be extended to the following:

- Monthly treatment group: -8 days to +15 days. Note, interval for consecutives injection must be at least 14 days.
- EOM treatment group: -8 days to +30 days for the first study year and -16 days to +30 days for the second study year

MASKING RULES

Due to current COVID-19 restrictions, clinical sites might encounter difficulties maintaining appropriate clinic staffing to satisfy the approved masking rules for the APL2-304 (Oaks) study. Based on this, and in an attempt to minimize the amount of missed data and IP administrations, Apellis is implementing a temporary adjustment to the study masking rules.

This temporary change must be approved by the Apellis Medical Director prior to implementation and must be documented via a temporary and modified Delegation of Authority Log. Each masked assessment performed by an unmasked staff and vice versa (even with Apellis approval and following the below guidelines) should be documented.

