#### All data except microperimetry

- If the subject completed Month 12 (Visit 14) assessments, then the data cutoff will be the day that the Month 12 (Visit 14) assessments are completed, regardless of Study Day.
- If the subject did not complete the Month 12 (Visit 14) assessments (e.g. missed or early terminated) then Study Day 375 (Study Day 360 (target date) + 15) will be used as the Month 12 cutoff.

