### 6.2.2. Main Analysis of Primary Efficacy Endpoint

The primary endpoint will be analyzed in the mITT population with subjects grouped according to the treatment assigned at randomization.

A MMRM model will be used to analyze the primary endpoint. The analysis model will include treatment (PM, PEOM, sham), presence of choroidal neovascularization in the fellow eye at baseline (Yes, No) and baseline GA lesion area ( $< 7.5 \text{ mm}^2$  or  $\geq 7.5 \text{ mm}^2$ ) as fixed effects, time (study month, categorical) as a factor, the time  $\times$  treatment interaction term, and the baseline GA lesion area ( $< 7.5 \text{ mm}^2$  or  $\geq 7.5 \text{ mm}^2$ )  $\times$  time interaction term. The least square [LS] mean change from baseline to Month 12 will be estimated from the model for each of three arms as well as the comparisons of each of the three arms to each other. For other time points of interest, LS mean change from baseline will be estimated and compared between treatments. For each estimated LS mean, the corresponding 95% CI will be presented based on the model. For the comparison of the LS means, the corresponding 95% CI and the 2-sided P-value along with the percentage difference (difference in LS means between the arms/the comparison group LS mean) will be

presented. A common unstructured covariance matrix will be used to model the within-subject errors, the sandwich estimator (Diggle, Liang, and Zeger 1994) will be used to estimate the standard errors of the fixed effects parameters, and the degrees of freedom will be partitioned into between-subject and within-subject portions. If there are convergence problems with the model, then a heterogeneous autoregressive (1) covariance matrix will be used. If convergence problems still exist, an autoregressive (1) covariance matrix will be used. The LS mean of the change from baseline in the total area of GA lesion(s)  $\pm$  the standard error will be plotted over time by treatment group.

The observed values for the total area of GA lesion(s) will be summarized by treatment group and visit for both the study and the fellow eye. Summaries will present the descriptive statistics for baseline, absolute values and change from baseline data by visit.

The mean change from baseline in the total area of GA lesion (s) in the study eye  $\pm$  the standard error will be plotted over time by treatment group.

All GA lesion (s) size data will be listed for the ITT set.

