#### **6.2.4.3. Rate of Change Analyses**

The mean rate of change in GA area (i.e., slope) will be compared between each pegcetacoplan arm and the pooled sham arm by use of linear mixed effects model assuming time as continuous and linear (“slope model”). The analysis model will include treatment (PM, PEOM, sham), presence of choroidal neovascularization in the fellow eye at baseline (Yes, No), baseline GA lesion area ( $< 7.5 \text{ mm}^2$  or  $\geq 7.5 \text{ mm}^2$ ) as fixed effects, time (study month, continuous assuming linearity), the time  $\times$  treatment interaction term as well as the baseline GA lesion area  $\times$  time interaction term. The response variable will be the GA lesion area. A common unstructured covariance matrix will be used to model the within-subject errors, the sandwich estimator will be used to estimate the standard errors of the fixed effects parameters, and the degrees of freedom will be partitioned into between-subject and within-subject portions. If there are convergence problems with the model, then a heterogeneous autoregressive (1) covariance matrix will be used. If convergence problems still exist, an autoregressive (1) covariance matrix will be used. The mean rate of change (slope), standard error, and confidence interval will be estimated for the baseline to Month 12 as well as the baseline to Month 6 and Month 6 to Month 12 periods for each treatment group. In addition, the estimated difference in slopes among the treatment groups along with the 95% CIs and p-value will be reported. The slopes and 95% CIs will be converted to an annualized rate of growth for each period and each treatment group.

The observed values for the total area of GA lesion(s) will be summarized by treatment group and visit for the baseline to Month 6 and Month 6 to Month 12 time periods. Summaries will present the descriptive statistics for baseline, absolute values and change from baseline to

Month 6 and change from Month 6 to Month 12 data. In addition, the annualized rate of growth for each time period will also be presented.

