### 1.2.3. Rate of Change Models

```
*****;
*** Rate of Change analyses ***;

* In this example, repeated measures are available at
* avisitn = 0 (baseline), 2 (Month 2), 4 (Month 4)
* 6 (Month 6), 8 (Month 8), 10 (Month 10) and 12 (Month 12)
*
* AVAL is the actual GA lesion measurement at the corresponding visit * for
the study eye from ADGA.
* SGALESAT is the GA lesion size (categorical) at baseline
* FCNVAT is the fellow eye CNV status at baseline
* TR01PG2N is the pooled treatment group (1 = PM, 2 = PEOM, 3 = Sham)
* T is equivalent to AVISITN
*
* The data is read in from ADGA
*****;
```

```
proc mixed data=ga method=reml covtest empirical;
```

```
class subjid TR01PG2N FCNVAT SGALESAT t;
model aval = SGALESAT TR01PG2N avisitn TR01PG2N * avisitn
          SGALESAT*avisitn FCNVAT/cl solution;
repeated t /type=un sub=subjid r ;

**Month 6;
estimate 'PM Month 0 to 6 slope' TR01PG2N*avisitn 6 0 0
          avisitn 6 SGALESAT*avisitn 3 3 /cl;
estimate 'PEOM Month 0 to 6 slope' TR01PG2N*avisitn 0 6 0
          avisitn 6 SGALESAT*avisitn 3 3 /cl;
estimate 'Sham Month 0 to 6 slope' TR01PG2N*avisitn 0 0 6
          avisitn 6 SGALESAT*avisitn 3 3 /cl;

estimate 'Month 0 to Month 6 Difference in slope PM - Sham'
          TR01PG2N*avisitn 6 0 -6 /cl;
estimate 'Month 0 to Month 6 Difference in slope PEOM - Sham'
          TR01PG2N*avisitn 0 6 -6 /cl;
estimate 'Month 0 to Month 6 Difference in slope PM - PEOM'
          TR01PG2N*avisitn 6 -6 0 /cl;

**Month 12;
estimate 'PM Month 6 to 12 slope' TR01PG2N*avisitn 6 0 0
          avisitn 6 SGALESAT*avisitn 3 3 /cl;
estimate 'PEOM Month 6 to 12 slope' TR01PG2N*avisitn 0 6 0
          avisitn 6 SGALESAT*avisitn 3 3 /cl;
estimate 'Sham Month 6 to 12 slope' TR01PG2N*avisitn 0 0 6
          avisitn 6 SGALESAT*avisitn 3 3 /cl;

estimate 'Month 6 to 12 Difference in slope PM - Sham'
          TR01PG2N*avisitn 6 0 -6 /cl;
estimate 'Month 6 to 12 Difference in slope PEOM - Sham'
          TR01PG2N*avisitn 0 6 -6 /cl;
estimate 'Month 6 to 12 Difference in slope PM - PEOM'
          TR01PG2N*avisitn 6 -6 0 /cl;

ods output diffs= diff2 LSMeans= LSMean2 CovParms = COV2
          estimates = estimates2;

**Month 0 to 12;
estimate 'PM Month 0 to 12 slope' TR01PG2N*avisitn 12 0 0
          avisitn 12 SGALESAT*avisitn 6 6 /cl;
estimate 'PEOM Month 0 to 12 slope' TR01PG2N*avisitn 0 12 0
          avisitn 12 SGALESAT*avisitn 6 6 /cl;
estimate 'Sham Month 0 to 12 slope' TR01PG2N*avisitn 0 0 12

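### The lesion-growth slope models treat nominal month as elapsed time, so late images inflate the annualized rate; the absence of a day limit on scheduled visits departs from protocol 12.10 and is not listed as a change

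*SAP*

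**What the plan says.** **Visit assignment.** SAP 13.4.1: "the actual scheduled nominal post-baseline visit will be used for over time summaries". Tables 5 and 6 give day ranges, but only for placing unscheduled and early termination visits. SAP 3.6 adds that for a subject who completed Month 12, "then the data cutoff will be the day that the Month 12 (Visit 14) assessments are completed, regardless of Study Day".

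**Time in the models.** The primary model (SAP 6.2.2) has "time (study month, categorical) as a factor". The supplemental slope model (SAP 6.2.4.3) has "time (study month, continuous assuming linearity", and its slopes are then converted to an annualized growth rate. The sample code in SAP Appendix 1.2.3 says "T is equivalent to AVISITN", so nominal month is both the regression variable and the repeated index.

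**Protocol rule.** Protocol 12.10 derives analysis visits for the primary endpoint from day windows and takes the visit closest to the target day. SAP section 15, which lists changes from the protocol's analyses, does not mention this.

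**Permitted timing.** In year 1 the window is ±8 days in both regimens (protocol Appendices A and C). In year 2 it is ±8 days for monthly and ±16 days for every other month (EOM). Protocol Appendix K extends the window for giving study drug during COVID-19 restrictions, with medical monitor approval: up to 15 days late in the monthly groups, and "EOM treatment group: -8 days to +30 days for the first study year and -16 days to +30 days for the second study year". The Window row of the COVID-19 tables stays at 8 days in year 1.

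**Schedule rows.** The Day row puts Month 12 at Day 360. The Week row above it reads "Week 0 0 4 8 12 16 20 24 28 32 36 40 44 48". Protocol 7.3.2 states: "If a subject falls outside the visit window for a dosing visit, the dose should be skipped".

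**The concern.** Lesion area grows steadily on the plan's own assumptions (2.13 mm² per year on sham), so measured change depends on days elapsed as well as on treatment. A repeated-measures model with categorical visit estimates change at the visit as attended. A slope model claims something else, growth per unit of time, and it is wrong to the extent that its time variable is wrong. If late imaging were also more common in one regimen than the other, part of a between-arm difference would be follow-up time. A reader of the protocol would expect day windows to limit this for the primary endpoint. The SAP drops them for scheduled visits without saying so.

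**Working it through.** **Inputs.** Growth 1.47 (pegcetacoplan monthly, PM), 1.70 (pegcetacoplan EOM, PEOM) and 2.13 (sham) mm² per year; SD 1.50 or 1.25 mm²; 200 per analysed group (protocol 12.5, SAP 3.4). Month 12 target is Day 360 (SAP 3.6). Pooled sham is half monthly, half EOM. Two-sided alpha is 0.0495 (power table) and 0.0496 (SAP 6.2.1).

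**Plan's own figure.** SE = 1.50 × √(2/200) = 0.15. Noncentralities are 0.66/0.15 = 4.40 and 0.43/0.15 = 2.87. A noncentral t with 597 df at 0.0495 gives 99.2% (PM) and 81.5% (PEOM), matching the stated values.

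**Slope model.** A scheduled Month 12 image on Day 390 is entered as 12 months of 30 days, that is 360 days. From baseline and that image alone, the rate is overstated by 390/360 − 1 = 8.3%; for Day 375 it is 375/360 − 1 = 4.2%. On-time images dilute this. In an equally weighted straight line through months 0, 2, …, 12 with only the last image 30 days late, the excess is (12 − 6)/Σ(t − 6)² = 6/112 = 5.4%. The planned model weights images differently, but the direction is the same.

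**Between-arm imbalance at Month 12, standard windows.** Both regimens have ±8 days, so the permitted difference is 0.

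**Between-arm imbalance, COVID-19 extension.** Assume every Month 12 image is at the late dosing limit: monthly Day 375, EOM Day 390, pooled sham mean 382.5. Each active arm is then 7.5 days from sham. The size depends on whose growth rate is applied to those days:

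| Rate applied | Calculation | mm² |
|---|---|---|
| PM | 1.47 × 7.5/365.25 | 0.030 |
| PEOM | 1.70 × 7.5/365.25 | 0.035 |
| Sham | 2.13 × 7.5/365.25 | 0.044 |

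The shift favours PM and works against PEOM. If 10% to 25% of subjects were at the limit (an assumption; the documents give no rate), the sham-rate figure becomes 0.10 × 0.044 = 0.004 to 0.25 × 0.044 = 0.011 mm².

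**What that does to the tests.** With no drug effect and everyone at the limit, 0.044 mm² is 0.29 SE at SD 1.50 and 0.35 SE at SD 1.25. Two-sided error for PM against sham goes from 0.0496 to 0.059 or 0.064. PEOM power at SD 1.50 (two-sample approximation) goes from 81.7% to 72.9%. At 10% to 25% of subjects, error is about 0.050 and PEOM power is 80.9% to 79.7%.

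**Month 24.** With all visits at the latest standard day (728 and 736, pooled sham 732), the gap from sham is 4 days: 2.13 × 4/365.25 = 0.023 mm².

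**Day and Week rows.** Month m is Day 30m but Week 4m, or 28m days, so the gap is 2m days. It is 8 days at Month 4, 10 days at Month 5 (150 against 140), 24 days at Month 12 (360 against 336) and 48 days at Month 24 (720 against 672). From Month 5 it exceeds ±8 days. The rows are the same in the monthly and EOM schedules.

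**The case against.** Categorical nominal-visit analysis is a legitimate primary method under a treatment policy strategy, and strict windowing has its own cost: under SAP Table 6 a Day 390 image in an EOM subject would fall in Month 14 and leave Month 12 empty. That stands, and the primary model need not change.

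The COVID-19 route to unequal follow-up is an inference. The extension is worded for study drug administration, the tables keep the 8-day visit window, visits are projected from Day 1, and dosing may fall on a different day from assessment. On the other side, images are to be taken before dosing on dosing days and assessments done on one day, so a late dosing visit can carry a late image. The documents neither settle nor quantify this.

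SAP 6.2.3.2 also plans PM against monthly sham and PEOM against EOM sham, which compares groups with the same permitted windows. That answers much of the imbalance question. It uses half the controls, though, and does not repair the annualized rates.

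A reader might infer that late visits make the PM effect 11% larger. With everyone at the late limit the PM contrast does move from 0.66 × 360/365.25 = 0.651 to (2.13 × 382.5 − 1.47 × 375)/365.25 = 0.721 mm². But a delay of 22.5 days in all arms already gives 0.66 × 382.5/365.25 = 0.691. Only the remaining 0.030 comes from unequal delay.

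**Conclusion.** The point holds and is minor. The definite fault is in the supplemental slope and piecewise slope models: they report a rate per year but use a visit label as time, with no day limit on the label. The error is up to about 8% of one subject's baseline-to-Month-12 rate for a 30-day-late image. The unlisted departure from protocol 12.10 is also definite.

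A between-arm effect on the Month 12 primary endpoint is only a possibility. As far as permitted timing goes, it needs the COVID-19 extension and imaging that follows the late injection. It is then at most about 0.03 to 0.04 mm² per contrast with every visit at its late limit, and about 0.01 mm² or less at an assumed 10 to 25%. The documents do not support saying that PM is in fact flattered. At Month 24 the standard windows do differ, but the SAP has removed Month 24 lesion growth from formal testing.

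A reader might also infer that the Day and Week mismatch gives the arms unequal growth time. It does not, because the rows are identical across regimens. It is a separate contradiction affecting all arms equally; nothing in the documents shows that any site scheduled from the Week row.

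**What to change.** 1. **Slope and piecewise slope models (SAP 6.2.4.3, Appendix 1.2.3).** Enter time as actual days from the baseline FAF to each FAF, on one stated scale, for example days/30 to match the SAP's 30-day months. Express the ESTIMATE multipliers, the Month 6 knot and the annualization factor on that scale. Keep nominal visit only as the REPEATED index.
2. **Reporting.** Tabulate actual study day of the Month 12 and Month 24 FAF by arm. Leave the primary model unchanged: adjusting it for deviation from target day would condition on something that happens after randomisation and may depend on regimen. List the departure from protocol 12.10 in SAP section 15.
3. **Visit schedules.** The Day and Week rows in protocol Appendices A to D and K, and in SAP Tables 9 to 16, must be reconciled so that each visit has one date, particularly as protocol 7.3.2 ties dosing to the visit window.

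The cost is a change to the slope code with its contrasts rechecked, one table, one line in section 15 and a schedule correction. No new data are needed.
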